6.3.1 Supplementary Tables for Schedule 1: PK, ADA, Cytokines / Dose Expansion

Table 14: Schedule 1 Dose Expansion PK, ADA, Cytokines (C1/D1 - 24 hrs post EOI)

Sample	SL-279252 PK Sampling (Expansion Cohorts) / Dosing Schedule 1 / Collect blood for PK at each time point unless otherwise specified ³				
	C1/D1		C1/D1 and C1/D2		
	Predose -30 min (\pm 5 min)	EOI (+ 5 min)	Time points relate to post EOI		
PK	X ¹	X ²	X	X	X
Cytokines	X ¹		X	X	X
ADA	X ¹				

1. Collect predose samples for ADA, PK and cytokines.
2. EOI sample should be collected within 5 minutes after stopping infusion. Date and clock time for start/stop of infusion as well as for sample collection (pre/post dose) will be recorded.
3. See the **SLM for the most accurate estimates of blood needed and for additional details on sample handling instructions**. Collect PK, ADA, cytokine sample in opposite arm rather than from infusion port for drug delivery.

Table 15: Schedule 1 Dose Expansion PK, ADA, Cytokines (C1/D15 and Beyond)

Sample	SL-279252 PK Sampling (Expansion Cohorts) / Dosing Schedule 1 / Collect blood for PK at each time point unless otherwise specified ³							
	C1/D15, C2/D1, C3/D1 and C4/D1 ⁴		C1/D15 & D16, C2/D1 & D2			C3/D1 and C4/D1 ⁴	D1 C7, C10, C13 and C25	Collect sample for PK/ADA within 7 - 30 days post last dose of SL-279252. If this sample is positive for ADA, then monthly testing for PK/ADA required until resolution of ADA to baseline.
	Predose -30 min (± 5 min)	EOI (+ 5 min)	Time point relates to post EOI			Time point relates to post EOI	Predose ⁵	
PK	X ¹	X ²	X	X	X	6 hr (±30 min)	-30 min (± 5 min)	
Cytokines (cycles 1 and 2 only)	X ¹		X ³	X ³	X ³			
ADA		X ¹						X

1. Collect predose samples for PK/ADA and cytokines. **See SLM for amount of blood needed and sample handling instructions.**
2. EOI sample should be collected within 5 minutes after stopping infusion. Date and clock time for start/stop of infusion as well as for sample collection (pre/post dose) will be recorded.
3. PK/cytokine analyses at EOI and post EOI time points indicated above on C1/D15, C1/D16, C2/D1 and C2/D2. The PK, ADA, cytokine sample **should not** be collected from infusion port for drug delivery i.e., recommend having a separate line in the opposite arm for PK, ADA and cytokine sample collection.
4. C3/D1 and C4/D1 collect a predose sample for PK/ADA and then EOI, and 6 hr post EOI sample for PK.
5. Collect a predose sample for PK/ADA analyses on D1 of cycles 7, 10, 13, and 25. If subject has positive ADA test on D1 of cycle 13, then follow up predose PK/ADA samples should be collected every ~90 days on D1 of subsequent treatment cycles until ADA resolves to baseline.

6.3.2 Correlative Sample Time points / Schedule 1 / Dose Expansion

Table 16: Complement, Immunophenotyping Sample Time Points

Dose Expansion Cohorts	C1/D1 & C2/D1			C1/D2 & C2/D2	C1/D5	C1/D8	C1/D15 & C2/D15			C1/D16 & C2/D16
Schedule 1	Predose (-90 to -30 min)	1 hr post EOI (±10 min)	2 hr post EOI (±10 min)	24 h post EOI (±2 hr)	96 h post EOI (±2 hr)	Predose (-90 to -30 min)	Predose (-90 to -30 min)	1 hr post EOI (±10 min)	2 hr post EOI (±10 min)	24 h post EOI (±2 hr)
Complement (SC5b-9) ¹	X	X		X			X (C1D15 only)	X (C1D15 only)		X (C1D16 only)
Immunophenotyping ¹	X			X	X	X	X			X
Receptor Occupancy ¹		X							X	

1. 1. Refer to SLM for details. Complement is NOT collected on C2D15 or C2D16.

6.4 SOA Table: Schedule 2 Dose Expansion Cohorts

Dosing Schedule 2		Once weekly (D1, D8, D15, D22) X 4 every 28 days																		Post Txt ^s	Follow Up ^t		
Cycle Length = 28 days		Cycle 1						Cycle 2						Cycle 3				≥ Cycle 4					
Procedures/ Assessments ^b	Screen ^a	D1	D2	D8	D15	D16	D22	D1	D2	D8	D15	D16	D22	D1	D8	D15	D22	D1/ D15	D8/ D22				
	Days -21 to -1	1	2	8	15	16	22	29	30	36	43	44	50	57 etc.	64 etc.	71 etc.	78 etc.	85 etc.	99 etc.	w/in 30 d			
Informed consent	X																						
Inclusion/exclusion criteria ^c	X	X																					
Demographics & medical history	X																						
Cancer treatment history	X																						
Physical examination	X	X		X	X			X	X									X	D1 only		X		
Pulse oximetry ^d	X	X ^{d1}		X ^d ₁	X ^{d1}			X ^{d1}	X ^{d2}				X ^{d2}					X ^{d2}			X		
Vital signs ^d	X	X ^{d1}		X ^d ₁	X ^{d1}			X ^{d1}	X ^{d2}				X ^{d2}					X ^{d2}			X		
Height	X																						
Weight	X	X			X			X			X			X			X		X		X		
ECOG performance status	X	X		X	X			X	X								X		X	D1 only		X	
Pregnancy test ^e	X		Every 8 weeks											X	Every 8 weeks						X		
Hematology profile ^f	X	X	X	X	X	X	X	X	X	X	X	X	X	X	X	X	X	X	X		X		
Chemistry profile ^f	X	X	X	X	X	X	X	X	X	X	X	X	X	X	X	X	X	X	X		X		
Ferritin		X																					
Coagulation profile ^g	X	X	X		X	X		X	X														
Thyroid test ^h	X							X										X ^h			X		
Antiviral testing (HBV/HCV) ⁱ	X																						
Cardiac:12-Lead ECG/ECHO ^j	X																						
Tumor imaging ^k	X		Every 8 weeks through week 24 (see footnote k)											X	(see footnote k)					X	X		
Sparse PK/immunogenicity/cytokine samples in Expansion cohorts ^L		X	X		X	X		X	X					X				X		X			
Complement ^m		X	X		X	X		X	X														
Immunophenotyping ^m		X	X	X	X	X	X	X	X	X	X	X	X										

Dosing Schedule 2		Once weekly (D1, D8, D15, D22) X 4 every 28 days																	Post Txt ^s	Follow Up ^t		
Cycle Length = 28 days		Cycle 1						Cycle 2						Cycle 3				≥ Cycle 4				
Procedures/ Assessments ^b	Screen ^a	D1	D2	D8	D15	D16	D22	D1	D2	D8	D15	D16	D22	D1	D8	D15	D22	D1/ D15	D8/ D22			
	Days -21 to - 1	1	2	8	15	16	22	29	30	36	43	44	50	57 etc.	64 etc.	71 etc.	78 etc.	85 etc.	99 etc.	w/in 30 d		
Receptor Occupancy ^m		X	X		X	X		X	X		X	X										
Cell-free nucleic acid (cfNA) ⁿ		X																				
SL-279252 administration ^o		X		X	X		X	X		X	X		X	X	X	X	X	X				
Concomitant medications	X	X	Continuous monitoring															X				
AEs/SAEs ^p	X	X	Continuous monitoring: Collect Ad hoc sample if IRR or CRS event occurs as outlined in Section 6.6.1 and SLM															X				
Archival tumor tissue ^q	X																					
Tumor biopsy ^r	X				X																	
Survival																			X			

Abbreviations: **Txt** = Treatment; **w/in**=within; **C** = Cycle; **D** = Day

- Screening:** Screening Period extends from Day -21 to Day -1. The following screening assessments must be performed within 72 hours of the first dose of SL-279252: hematology profile, chemistry profile, coagulation profile, pregnancy test. Baseline CT or PET/CT or MRI tumor assessments are required for all subjects within 28 days prior to enrollment. Subjects will be enrolled based on local PD-L1 tumor testing results. Any PD-L1 tumor testing results prior to enrollment are acceptable.
- Assessment Window:** A physical exam, weight and ECOG performance status obtained for a subject within 24 hours prior to dosing on Cycle 1, Day 1 is acceptable. With exception of Screening assessments and unless otherwise specified, assessments performed at \leq 3-week intervals will have a +/- 3-day window and assessments performed at $>$ 3-week intervals will have a +/- 1-week window. Assessments throughout the study are calendar based starting from the first day of dosing (day 1) in the first treatment period. Dose interruptions should not alter the assessment schedule for any subsequent treatment period.
- Inclusion/Exclusion criteria:** Subjects must meet eligibility criteria prior to first dose of SL-279252 on C1/D1.
- Vital Signs:** BP, HR, T and RR must be measured after the subject has been sitting for at least five minutes. Pulse oximetry will be collected to coincide with vital sign time points noted below.
 - Collect vital signs during Cycle 1 on Day 1, D8, D15, D22:** Predose (within 30 min of starting the infusion) and 15 min (\pm 5 min), 0.5 hr (\pm 5 min), 1 hr (\pm 10 min), 1.5 hr (\pm 10 min) and 2 hr (\pm 10 min) **after SOI**.
 - Collect vital signs on dosing days (Cycles \geq 2, Days 1 and 15):** Predose (within 30 minutes of starting the infusion) and at the EOI (\pm 2 min)
- Pregnancy Test:** A serum pregnancy test (β -hCG) or urine pregnancy test must be performed at screening for all females who are of childbearing potential within 72 hrs of starting SL-279252. Repeat this test every 8 weeks during SL-279252. *Contraception should be continued for at least 30 days after the last dose of SL-279252.*
- Clinical Laboratory Tests (Hematology/Clinical Chemistry):** Clinical laboratory tests will be performed at local laboratories according to the laboratory's normal procedures. See Section 6.6.6 for list of laboratory tests required.

- g. **Coagulation Tests:** PT, INR, APTT, fibrinogen, d-dimer (the latter test at screening and then as needed for clinical assessment)
- h. **Thyroid Function Test:** TSH, and free T4 tests will be performed at screening, C2D1, C3D1, C4D1 and then every 8 weeks.
- i. **Antiviral Testing:** Please see exclusion criterion 17 in Section 4.3.
- j. **Cardiac Assessments (obtain within 28 days of first dose):** 1) **ECG:** 12-lead ECG reading must be performed at screening to serve as baseline for comparison with ECG obtained for safety reason. 2) **ECHO:** An ECHO must be performed at screening to serve as baseline for comparison with ECHO obtained for safety reason.
- k. **Tumor Assessment:** Tumor assessments are required for all subjects within 28 days prior to enrollment. Baseline and on-treatment tumor assessments for solid tumors by iRECIST should include CT with contrast of chest, abdomen, and pelvis and other known sites of disease at each time point. Bone scan and positron emission tomography (PET)/CT should be performed only if clinically indicated. Baseline and on-treatment tumor assessment for lymphoma by RECIL 2017 should be done using CT scan with contrast and PET/CT of neck, chest, abdomen, and pelvis and other known sites of disease at each time point. Please refer to Section 8 for requirements regarding disease assessment. Tumor assessments must be performed at screening and at the following intervals until disease progression is confirmed: approximately every 8 weeks through Week 24 (e.g., C3D1, C5D1, C7D1), every 12 weeks up to year 2 (prior to cycles 10, 13, 16, 19, 22, 25, 28 and 31), and then every 6 months (prior to cycles 37, cycle 43, etc.) up to conclusion of the study. Confirmatory scans should be performed at least 4 weeks (>28 days), but no longer than 8 weeks after initial documentation of an objective response. Subjects who discontinue study treatment for reasons other than disease progression (e.g., AE or withdrawal of consent) will be monitored for radiologic response until start of another anti-cancer therapy, or disease progression, withdrawal of consent or death.
- l. **Sparse PK and immunogenicity (i.e., ADA) and cytokine sampling (Dose Expansion Cohorts):** PK, ADA, and cytokine time points for collection are outlined in supplementary PK tables in Section 6.4.1 (Table 17 and Table 18). Blood volumes required are provided in the SLM. PK, ADA, cytokine samples should not be collected from infusion port for drug delivery i.e., recommendation is to use a separate line in the opposite arm for sample collection. If subject has positive ADA test on D1 of cycle 13, then follow up predose samples for PK/ADA should be collected every ~90 days on D1 of subsequent treatment cycles until ADA resolves to baseline. If ADA positivity is detected within 7-30 days after the last dose of SL-279252, then follow up testing for PK/ADA should be performed at monthly intervals until ADA resolves to baseline.
- m. **Correlative laboratory studies:** Refer to supplementary Table 19 for details in Section 6.4.2 plus the SLM.
 - *Complement*
 - *Immunophenotyping and receptor occupancy*
- n. **cfNA:** Collect blood into 2 separate cfNA Streck tubes and invert to mix thoroughly as described in SLM.
- o. **SL-279252 Administration:** SL-279252 should be administered on D1, D8, D15, and D22 according to the prescribed dosing schedule without deviation in cycle 1 to align with the safety assessment and sample (PK, ADA, etc.) collection schedules. Beginning on cycle 2, day 1, a window of +/- 1 day is allowed for scheduled dosing days for drug administration.
- p. **AE Monitoring:** Subjects will be followed continuously for AEs during the study and for 90 days after the last dose of IP. After a subject is discontinued from SL-279252 due to progressive disease or for other reasons, any ongoing AE should be followed until resolution (or return to baseline) and documented in the eCRF. If another anti-cancer agent is started, only SAEs and AEs that occur prior to starting the new anticancer therapy should be recorded. In the event of a continuing SAE or a non-serious AE, the subject will be asked to return for follow-up until the SAE or AE has resolved or is deemed to be continuing indefinitely. AEs will be characterized per NCI-CTCAE criteria v5.0 and events recorded in the eCRF.
 - Ad hoc blood samples for clinical safety labs should be collected for AE related to IRR and/or CRS events as noted in Section 6.6.6.1.
- q. **Archival tumor tissue (from most recent biopsy):** Provide FFPE tissue on slides (recommend a minimum of 10 slides) or a block of FFPE tissue (the latter is preferred). Refer to Section 6.9.2.2 and the SLM for details.

- r. **Tumor Biopsy:** Paired biopsies (pre- and on-treatment) obtained in subjects who have tumor accessible to core-needle biopsy. The on-treatment biopsy should be obtained during the first cycle on or between D16-D23. On-treatment biopsies of responding or progressing lesions may be obtained for further characterization of the changes in the TME. **Please refer to Section 6.9.2.1 and SLM for details regarding biopsy.**
- s. **Post-Treatment:** A Post-Treatment visit will be conducted within 30 days (± 3 days) after the last dose of SL-279252, or prior to the start of a new therapy, or at the end of study, or if the subject's participation is terminated early. See AE monitoring footnote above.
- t. **Follow-Up:** All subjects will be contacted after discontinuing study therapy to collect survival status. Subjects should be contacted every 3 months (+/- 14 days) until death, withdrawal of consent or subject is lost to follow-up. Contact may include clinic visit, telephone contact, email or mail to document survival status.

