3.5.1 Management of Infusion-related Reactions

The data from the NHP studies indicate a potential risk for IRRs including CRS in humans dosed with SL-279252. The IRRs that were noted in cynomolgus monkeys were potentially cytokine-mediated as they a) demonstrated dose dependence and b) the severity of clinical symptoms correlated with cytokine level increases in the peripheral blood. It is important to note that the reactions that were noted in monkeys occurred during or immediately after SL-279252 infusion. Given the mechanism of action of SL-279252 (T cells become activated as they recognize tumor antigen), rapid onset of IRRs would be expected but the possibility of delayed reactions cannot be excluded. It is unlikely that SL-279252 infusion reactions are antibody-mediated type I or type 3, allergic HSRs as these reactions would not be expected to demonstrate dose dependence.

Differentiating between IRRs that are due to either the common non-allergic HSRs (e.g., CRS) or the rarer allergic HSRs can be challenging due to overlapping clinical manifestations. There are no specific clinical features (including symptoms and timing of reaction) that can absolutely distinguish between these two entities.

General guidance is provided below for IRRs secondary to both allergic and non-allergic HSRs e.g., CRS. These guidelines are not meant to be prescriptive. Established institutional guidelines should be followed where appropriate.

At the resolution of the event, the entirety of the data including clinical symptoms, response to treatment and laboratory studies should be re-evaluated to determine the final etiology of the event. For purposes of standardized reporting, utilize terms based on best medical judgement of the AE/SAE and the definition found in NCI-CTCAE v5.0 for IRR, allergic reaction, anaphylaxis, and CRS.

Primary prophylaxis against IRRs is not permitted to avoid obscuring a potential safety signal and to enable an assessment of whether pre-medications should be required for all subjects. However, as noted in the guidance below, secondary prophylaxis (i.e., prevention of IRRs following an initial episode) is appropriate and permitted at the discretion of the investigator.

NOTE: In the event of any Grade IRR (including CRS), subjects will be admitted for closer observation until resolution of symptoms.

Adverse Event	General Guidance for Infusion-related Reactions (IRRs) [Rosello, 2017; Porter, 2018]			

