Infusion or Hypersensitivity Reactions		
Acute reactions to the IV administration of biologic agents is not uncommon. Reactions are either allergic reactions to foreign proteins or non-immune reactions. The term HSR is used to describe objectively reproducible signs or symptoms initiated by exposure to a defined stimulus at dose tolerated by a normal person. Allergy is HSR initiated by specific immunological mechanisms. Anaphylaxis is a severe, life threatening HSR. CRS consists of a non-allergic, cytokine mediated HSR. Differentiation between the common non-allergic HRS reactions and the rarer allergic HSR reactions can be challenging due to overlapping clinical manifestations. Fever, chills, rigors, headache, arthralgias, back pain, abdominal pain, nausea, vomiting, diarrhea, dyspnea, flushing, pruritus, and changes in heart rate and blood pressure are manifestations of common acute infusion reactions. Proinflammatory cytokines such as TNF-α and IL-6 may play a role in these reactions. Symptoms more suggestive of allergic HSR include generalized pruritus, urticaria, wheezing, frequent coughing, and anaphylactic symptoms. Subjects must be monitored for signs and symptoms of IRRs with prompt institution of treatment.
		
		
  
 Severity	Management	
  
	Severity	Management
Severity	Management			
		
  
 Grade 1	 
 Infusion interruption not indicated Admit to hospital for close observation until resolution of symptoms. Consider pre-medication (antipyretics, histamine (H)1 and H2 anti-histamines) for subsequent infusions per investigator/institutional guidelines 	
  
	Grade 1	
 Infusion interruption not indicated Admit to hospital for close observation until resolution of symptoms. Consider pre-medication (antipyretics, histamine (H)1 and H2 anti-histamines) for subsequent infusions per investigator/institutional guidelines
Grade 1	
 Infusion interruption not indicated Admit to hospital for close observation until resolution of symptoms. Consider pre-medication (antipyretics, histamine (H)1 and H2 anti-histamines) for subsequent infusions per investigator/institutional guidelines 			

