5.6 Monitoring Dose Administration

SL-279252 must be administered in an outpatient oncology treatment center or inpatient unit to enable close monitoring of subjects and proactive management of AEs. As SL-279252 contains only human protein sequences, the chance for SL-279252 to be immunogenic and induce allergic HSRs should be low. However, as with any biologic therapy, infusion or allergic HSRs are possible. Based on the pre-clinical toxicology studies, it is anticipated that subjects could also be at risk to develop CRS. Therefore, appropriate drugs and medical equipment to treat acute HSRs and monitoring and management of CRS must be immediately available, and study personnel must be trained to recognize and treat these toxicities. Subjects will be monitored prior to, during, and after infusion of SL-279252. Vital signs will be measured as outlined in the Schedule of Assessments (SOA) in Section 6 and as needed. In the event of any Grade IRR (including CRS), subjects will be admitted for closer observation until resolution of symptoms.

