 - 1) **Collect vital signs/pulse oximetry during Cycle 1 on D1, D8, D15, D22 and Cycle 2 D1 and D8:** Predose (within 30 min of starting the infusion) and 15 min (\pm 5 min), 0.5 hour [hr] (\pm 5 min), 1 hr (\pm 10 min), 1.5 hr (\pm 10 min) 2 hr (\pm 10 min), 4 hr (\pm 10 min) , and 6 hr (\pm 10 min) **after SOI**.
 - 2) **Vital signs/pulse oximetry should be taken once prior to scheduled PK samples on C1D2, C1D3, C1D4, C1D5, C1D16 and C2D2**
 - 3) **Collect vital signs/pulse oximetry on dosing days \geq C2D15:** Predose (within 30 min of starting the infusion) and at the end of infusion [EOI] (\pm 2 min)
- e. **Pregnancy Test:** A serum pregnancy test (β -hCG) or urine pregnancy test must be performed at screening for all FCBP within 72 hrs of starting SL-279252. Repeat this test every 8 weeks during SL-279252. *Contraception should be continued for at least 30 days after the last dose of SL-279252.*
- f. **Clinical Laboratory Tests (Hematology/Clinical Chemistry):** Clinical laboratory tests will be performed at local laboratories according to the laboratory's normal procedures. See Section 6.6.6 for list of laboratory tests required.
- g. **Coagulation Tests:** PT, INR, APTT, fibrinogen, d-dimer (the latter test Cycles 1 and 2 only)
- h. **Thyroid Function Test:** TSH, and free T4 tests will be performed at screening, C2D1, C3D1, C4D1 and then every 8 weeks.
- i. **Antiviral Testing:** Please see exclusion criterion 17 in Section 4.3.

j. **Cardiac Assessments (obtain within 28 days of first dose):** 1) **ECG:** 12-lead ECG reading must be performed at screening to serve as baseline for comparison with ECG obtained for safety reason. 2) **ECHO:** An ECHO must be obtained at screening to serve as baseline for comparison with ECHO

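### The Schedule 2 expansion table limits vital signs and pulse oximetry from cycle 2 to Days 1 and 15, although drug is also infused on Days 8 and 22

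*Protocol*

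**What the plan says.** The header of Protocol 6.4 gives the dosing as "Once weekly (D1, D8, D15, D22) X 4 every 28 days", and footnote o repeats it: "SL-279252 should be administered on D1, D8, D15, and D22 according to the prescribed dosing schedule". Footnote d sets the timing of vital signs and states that pulse oximetry coincides with them. Item 1 covers all four cycle 1 infusions, from predose to 2 hours after the start of infusion. Item 2 covers later cycles with a predose and an end-of-infusion reading: "Collect vital signs on dosing days (Cycles \geq 2, Days 1 and 15".

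Three other places bear on this:

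- **Protocol 6.3 (Schedule 1 expansion), footnote d item 2**, has the same wording.
- **Protocol 6.2 (Schedule 2 escalation), footnote d**, has an intensive set ("Collect vital signs/pulse oximetry during Cycle 1 on D1, D8, D15, D22 and Cycle 2 D1 and D8") and then a lighter predose and end-of-infusion set ("Collect vital signs/pulse oximetry on dosing days \geq C2D15").
- **Protocol 6.6.4** sends sites to footnote d for when to take vital signs, and **5.6** defers to the same tables: "Vital signs will be measured as outlined in the Schedule of Assessments (SOA) in Section 6 and as needed".

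**The concern.** Item 2 speaks of dosing days but then lists only half of them. On Schedule 1 the list is complete, because dosing from cycle 2 is on Days 1 and 15. On Schedule 2 it leaves out Days 8 and 22. No other section schedules a reading on those days from cycle 2 onward.

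Infusion-related reactions and cytokine release are the main anticipated risks of this drug. Section 3.5.1 notes that the "reactions that were noted in monkeys occurred during or immediately after SL-279252 infusion", and that "changes in heart rate and blood pressure are manifestations of common acute infusion reactions". The end-of-infusion reading falls in that window, with the predose reading as its reference. Without scheduled readings, what is recorded on Days 8 and 22 will depend on local habit. Schedule 2 is also the more frequent regimen: the longer interval on Schedule 1 is described in 3.2.3 as a way to mitigate toxicity. As written, the more intensive regimen has the smaller share of its infusions covered by scheduled readings.

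**Working it through.** The plan states no figure to reproduce, so the check is a count of infusions against scheduled reading days. Six cycles is an illustrative assumption; the protocol fixes no number of cycles.

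**Per cycle from cycle 2, Schedule 2 expansion (6.4)**

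- Infusions: Days 1, 8, 15, 22 = 4.
- Named in footnote d item 2: Days 1 and 15 = 2.
- Without a scheduled reading: 4 − 2 = 2, or 50%.

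**Over six cycles**

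| Table | Infusions | Covered by scheduled readings | Not covered |
|---|---|---|---|
| 6.4, Schedule 2 expansion | 6 × 4 = 24 | cycle 1: 4; cycles 2–6: 5 × 2 = 10; total 14 | 24 − 14 = 10 |
| 6.2, Schedule 2 escalation | 6 × 4 = 24 | item 1: 4 + 2 = 6; item 3: 2 (C2D15, C2D22) + 4 × 4 = 18; total 24 | 0 |
| 6.3, Schedule 1 expansion | 3 + 5 × 2 = 13 | item 1: 3; item 2: 5 × 2 = 10; total 13 | 0 |

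**Sensitivity to the number of cycles.** For n cycles the uncovered share in 6.4 is 2(n − 1)/(4n):

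- n = 2: 2/8 = 25%
- n = 6: 10/24 = 41.7%
- n = 12: 22/48 = 45.8%

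The share approaches 50% as n grows. The first uncovered infusion is C2D8, the sixth dose.

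**Choice or slip?** Expansion monitoring is deliberately lighter than escalation monitoring: cycle 1 readings stop at 2 hours in 6.4, against 6 hours in 6.2. But in 6.3 the lightening reduces readings per infusion and omits no infusion. Only 6.4 omits infusions, it gives no reason, and its wording matches 6.3. That pattern fits text carried over from Schedule 1 better than a decision.

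**The case against.** The strongest reply has four parts.

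1. **General monitoring applies regardless.** Section 5.6 requires subjects to be monitored before, during and after infusion, without limit by day or cycle. Sections 5.2.3 and 5.5 require a physician on site or immediately available, with resuscitation facilities, at every administration. This stands, and it narrows the point: the gap is in timed, recorded readings. A severe reaction would usually be clinically evident without them.

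2. **The grid may show the readings.** The 6.4 grid is broken in the available text. Its drug-administration row carries a single mark for cycle 4 onward, where there are two columns and drug is given on all four days, so that mark must span both. The vital-sign rows may be merged in the same way. If so, the table schedules the readings and the footnote's parenthesis is stale. This cannot be settled from the text. It changes the diagnosis but not the remedy: the footnote would contradict its own table, and 6.6.4 directs sites to the footnote.

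3. **No planned analysis depends on it.** SAP 11.4 presents vital signs only in a listing. The expansion stopping boundaries (Protocol 9.2.2) count Grade 3 or higher infusion-related reactions and discontinuations due to toxicity, both of which come from continuous adverse-event monitoring. This also stands. The consequence is for subject monitoring and completeness of the safety record, not for a decision rule.

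4. **It may never apply.** Schedule 2 must be opened and then be the one schedule taken into expansion, and Protocol 9.2.1.2 expects only Schedule 1 to be evaluated. That limits the importance of the point but does not make the footnote right.

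It is also true that expansion uses doses already cleared in at least 6 subjects, and that all four cycle 1 infusions, including the third dose at which monkey reactions first appeared, have the fuller set of readings.

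**Conclusion.** The concern holds. Footnote d item 2 of 6.4 names two of the four infusion days that apply from cycle 2, and nothing else in the protocol schedules readings on the other two. Taken literally, half of the infusions from cycle 2 have no scheduled vital signs or pulse oximetry: 10 of 24 over six cycles, against 0 of 24 in Schedule 2 escalation and 0 of 13 in Schedule 1 expansion.

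The size rests on reading the footnote as written and on the six-cycle illustration; the per-cycle figure of 2 in 4 does not depend on the latter. The practical risk is moderated by the general monitoring in 5.6 and depends on Schedule 2 reaching expansion. The text should still be corrected: it is a safety-monitoring instruction that is either wrong or at odds with its own table.

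**What to change.** Amend footnote d item 2 of Protocol 6.4 to cover cycle 2 onward on Days 1, 8, 15 and 22 (or simply all dosing days), keeping the predose and end-of-infusion readings. Make the vital-sign and pulse-oximetry rows of the 6.4 grid agree with it. Leave 6.3 unchanged, since it is correct for Schedule 1.

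The cost is two readings at each Day 8 and Day 22 infusion visit: 2 × 2 = 4 per subject per cycle, taking the total from 4 to 8. Over six cycles that is 10 × 2 = 20 per subject, or at most 15 × 20 = 300 in a full expansion cohort of 15. No visit or procedure is added. If the omission was in fact intended, the protocol should say so and give the reason.
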